## 1 Introduction

#### 1.1 Background

Triggerise has designed a web and phone based platform Named 'Tiko Explore' to digitally empower young girls and women in lower-income groups at scale, and connect them to the products, services and information that will improve their health and wellbeing, supporting local economies and building private sector service provider networks in the process. Triggerise employs a digital platform that connects consumers to health clinics, pharmacies, mobilizers and local small businesses—giving them both the power to access health information and services on their own terms. Building on these relationships, the platform uses principles of behaviour economics to motivate consumers to make positive choices by providing incentives and discounts, rewarding continued use of products etc.

Employing tried and tested marketing principles - including rewards, promotions, discounts, coupons, reminders, alerts etc., the platform has encouraged over 85,000 young women Rajasthan, Uttar Pradesh and Delhi to take up almost 150,000 sexual, reproductive and maternal health services. By linking the demand and supply sides of the market, our platform grows Sexual Reproductive Health (SRH) and maternal and child health (MCH) demand while enhancing user choice.

Example of (SRH) services and products include: (a) contraceptives such as OTC pills, condoms, diaphragm, etc; (b) family planning services such as medical counselling, IUD insertion/removal, etc; and (c) hygiene products such as sanitary pads. Example of MCH ) services include: (a) linking with medical professionals/gynaecologists for ANC check-up, laboratory testing; (b) linking to pharmacy for IFA and other supplements as prescribed by doctors; and (c) OTC products for mother and children from pharmacy.

The users use Tiko card to get substantial discounts as well as earn 'Tiko miles' which are redeemable as payment towards above products. The Pro agent is also allowed to buy hygiene products at bulk and at heavy discounts and sell them to beneficiaries. More information about the Tiko Platform (the intervention or the programme) is given in **Annexure 4**.

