- 2. Stratify sample as 500 non-users (enrollment minus users) and 1500 users
- 3. Distribute sample in proportion to the actual numbers as below.

City	Non-users	Actual Users	Total
Agra	347	527	873
Jaipur	28	691	719
Ajmer	75	110	184
Tonk	32	97	128
Delhi	19	76	95
Total	500	1500	2000

- 4. Obtain a list of randomly sampled Beneficiaries as above. We will obtain 10-times the number of completed interviews required per agent because our scoping visit suggests to expect 10-15% response rate in phone surveys. If required, Triggerise will make available more beneficiaries (their name and phone numbers per agent) if the sample size is not achieved.
- 5. NEERMAN enumerators will call each beneficiary sequentially in the list and fix appointments for the phone interview. The phone records will track validity of numbers, refusals and consents. Pro agent's help will be sought to establish our enumerators' bona fides if needed.

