Quantitative data with CAPI/CATI will only display name to the interviewer but the raw data will automatically deidentify/mask any identifiable data before it is shared with researchers for analysis. Only a single data manager will be responsible to keep survey data and linked identities of respondent (name and phone number) as two separate files in a non-networked computer under password protection. This data will be deleted three months after study completion. The data transmission between devices and data security on CAPI server follow 16-key encryption and comply with IT Act of India 2012.

**COVID-19 Related Infections** – The risk is a possibility during in-person interactions but we will adhere to ICMR guidelines on minimizing this risk such as use of a mask, sanitization of hands and tablets before/after interview, and maintaining a distance of 4-6 feet during interviews. Every enumerator will be given a covid-19 test 2-3 days prior to start of field work begins. Everyday morning and evening oximeter and temperature checks for enumerators will be done. Respondents will not be interviewed if they report flue like symptoms or report having COVID-19 in 2 weeks preceding the survey.

**Benefits of participation:** There will not be any monetary benefits to the survey participants, but they will be told that their participation helps in greater social good of improving the platform, scaling it up and sustaining it which can benefit others like them. However, we seek IRB permissions to in-kind care package for phone survey participants to ensure higher response rate. We are planning to offer a care package in form of Tiko miles (equivalent of money they can spend with linked service providers) or phone recharge coupon, etc.

**Consent Administration:** The consent form for quantitative and qualitative survey respondents are attached as **Annexure 7 and 8**. These consent forms clearly discuss survey purpose and methods, above risks and benefits, rights of respondents, and contact information of the IRB and ethics officer at NEERMAN who can be contacted in case of

grievances. We will record the consent in the tablet or on printed consent form with their (digital or actual) signature along with enumerator as a witness. In case a respondent refuses to sign the consent, then we will administer a verbal consent only but audio record it and get signature of a third party witness.

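### The phone-survey reward is left open between the evaluated platform's own currency and a neutral coupon; miles could tilt the user sample towards engaged women, by an unknown amount

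*Protocol*

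**What the plan says.** Protocol section 3, under the benefits of participation, states: "we seek IRB permissions to in-kind care package for phone survey participants to ensure higher response rate". It goes on: "We are planning to offer a care package in form of Tiko miles", which it describes as equivalent to money at linked service providers, and ends the list with "or phone recharge coupon, etc". It neither chooses between the options nor requires the same reward for users and non-users.

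Section 1.1 explains what the miles are. Women who use the Tiko card "earn 'Tiko miles' which are redeemable as payment towards above products". The same section describes rewards as one of the means by which the platform motivates use.

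Section 2.3 sets the phone sample at 500 non-users and 1,500 users. On response, it says "our scoping visit suggests to expect 10-15% response rate in phone surveys", and therefore: "We will obtain 10-times the number of completed interviews required per agent". If targets are not met, the sponsor supplies more names. The user target is divided by city but not by intensity of use.

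Section 2.2 says the data will be used to compare regular users with one-time users or non-users. Section 1.3 asks how often women use the platform, what they like about it, and whether they would use it again or recommend it.

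**The concern.** A survey reward should be equally attractive whatever the respondent's exposure. Miles may not be. The only use the protocol names for them is with linked providers, and a woman who already visits those providers may value them more than one who used the platform once. If so, willingness to be interviewed depends on engagement, which is what the survey sets out to describe.

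The replacement rule does not correct this. Women who do not respond are replaced by others from the list until the target is full, and within the user stratum nothing restores the balance of regular to one-time users. A low expected response rate leaves ample room for such selection.

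Two further effects are possible. Payment in the platform's own currency may prompt kinder answers to questions on satisfaction and recommendation. Separately, sections 2.1 and 2.6 feed backend transactions into the cost-effectiveness models. Miles paid for an interview and later redeemed could appear there as ordinary use if the data are extracted after the survey.

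**Working it through.** **The plan's own figure.** Contacts needed = completed interviews / response rate. At 10%, 2,000 / 0.10 = 20,000, which is 10 times the completes. At 15%, 2,000 / 0.15 = 13,333, or 6.7 times. The tenfold list matches the lower end of the stated rate.

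**What the targets rule out.** Completed interviews are fixed at 500 non-users and 1,500 users. (Section 2.1 gives 600 and 1,200, but either pair fixes the split.) A reward cannot change that ratio if the targets are met. What it can change is who responds within a stratum.

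**Sensitivity within the user stratum.** The documents give no response rates by engagement, so every input here is assumed:
- s = 0.35, the true share of regular users among users;
- a practice at 60% in regular users and 40% in the others;
- r, the response rate of regular users divided by that of the others.

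Achieved share = s·r / (s·r + 1 − s). Pooled estimate = 0.40 + 0.20 × achieved share. The true pooled value is 0.40 + 0.20 × 0.35 = 47.0%.

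| r | Achieved share of regular users | Pooled estimate | Bias |
|---|---|---|---|
| 1.0 | 0.350 | 47.0% | 0 |
| 1.1 | 0.385 / 1.035 = 0.372 | 47.4% | +0.4 pp |
| 1.5 | 0.525 / 1.175 = 0.447 | 48.9% | +1.9 pp |
| 2.0 | 0.700 / 1.350 = 0.519 | 50.4% | +3.4 pp |

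The overall response rate does not enter the formula; only the ratio r does. The bias is the same at 10% and at 15%.

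**Yardstick.** The affected quantity is the user estimate, so n = 1,500. The 95% margin is 1.96 × √(0.25 / 1,500) = 2.5 pp. With the design effect of 1.25 that section 2.2 applies to the in-person sample, it is 2.5 × √1.25 = 2.8 pp. Under these assumptions the bias stays below the margin at r = 1.5 and exceeds it at r = 2.

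**What is due to miles.** Engaged women may answer a call about Tiko more readily under any reward. The relevant quantity is the bias under miles minus the bias under a coupon. If, say, r were 1.1 with a coupon and 1.5 with miles, the part due to miles would be 1.9 − 0.4 = 1.5 pp. The documents give neither ratio.

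**The case against.** The strongest reply is that nothing is fixed yet. Ethics permission is still being sought and the neutral coupon is already in the same sentence. That is true, and it makes the change easy. It does not answer the point, because miles remain a live option.

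It can also be said that the lower appeal of miles to less engaged women is only an inference. That stands. Section 3 calls miles equivalent to money, the products listed in section 1.1 include everyday items such as sanitary pads, and the non-users are already enrolled. The appeal to engaged women is a possibility that follows from where miles can be spent; it is not a documented fact.

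The study is exploratory, and section 2.1 gives the phone survey a confirming role beside in-person interviews for which no care package is planned. This limits the weight of the point.

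Three stronger readings are tempting, and the documents do not support them:
- A reader might infer that the reward distorts the balance of users to non-users. The stratum targets prevent that.
- A reader might infer that miles draw non-users onto the platform and so bias who responds. Any such uptake would follow the interview and cannot affect who was interviewed or what was recorded. It matters only for later backend data.
- A reader might infer that, at 10-15% response, the reward largely decides the sample. That rate comes from a scoping visit, the reward is meant to raise it, and invalid numbers are part of the loss. A woman who is never reached is not influenced by any reward.

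Finally, a changed mix of regular and one-time users moves the pooled user figure. By itself it does not bias a contrast that keeps the two groups apart.

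**Conclusion.** The point holds in a limited form. The protocol leaves open paying phone respondents in the currency of the platform it evaluates. That is an avoidable source of selection within the user stratum and of favourable answering. The likely direction for pooled user estimates is upward, provided regular users score higher and respond more readily.

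The size is unknown. The range of +0.4 to +3.4 pp rests wholly on the assumed 35% share, the assumed 60% and 40%, and response ratios of 1.1 to 2. It also counts selection that a coupon might cause too. At the top it slightly exceeds the 2.5 to 2.8 pp margin; at the bottom it is trivial. It should be read as a sensitivity range, not as an estimate of harm. The backend effect is a separate possibility that depends on when the transaction data are extracted.

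**What to change.** In section 3 and in the ethics request, delete Tiko miles and the open-ended wording. Name one platform-neutral reward, the recharge coupon already listed, of equal value for users and non-users, and offer it without reference to platform rewards. This also keeps survey payments out of the backend transaction data.

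The cost is one line of text and possibly a small cash outlay for the coupons. It needs to be settled before fieldwork, because selection caused by the reward cannot be undone afterwards.

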## 4 Field Organization

We will recruit 3 teams of 9 enumerators and 1 supervisor in each of the four cities for quantitative surveys. Moreover, 15 CATI enumerators will be recruited who will work from Delhi/Mumbai office for phone surveys. These teams will be managed by a dedicated field coordinator and a senior field manager. There will be one senior field managers present throughout the field work and their executives will shift between two cities. The researchers will be involved throughout the training and first 2-3 days of field work and they will conduct random audit visits in between. The overall organization is depicted below.
